## 16.3 Statistical Consideration

Descriptive statistics, such as mean, standard deviation, and range for continuous variables, and percent and number for categorical variables, will be summarized for baseline information and demographic information. The statistical test for primary efficacy endpoint ORR will be performed using an exact binomial test for single proportion at the 5% one-sided significance level if appropriated.

## 16.4 Stopping rules for toxicity and futility

In the event of a death on study that is deemed to be possibly, probably, or definitely attributable to the drug, further infusions will be suspended pending review by the DMC and consultation with the FDA. To further protect the safety of subjects, the study incorporates a stopping rule if the lower bound of a 1-sided 80% exact binomial confidence interval of the discontinuation rate due to medically significant Grade 3 or greater events that are possibly, probably, or definitely attributable to the drug is > 20%. Operationally, any of the following would trigger such a rule: 2 out of the first  $\leq 6$  subjects or 3 out of the first  $\leq 9$  subjects or 4 out of the first  $\leq 13$  or 5 out of the first  $\leq 16$  or 6 out of the first  $\leq 20$  subjects have unacceptable toxicity or  $\geq$  Grade 3 AEs that are possible, probably, or definitely attributable to

drug. If the true probability of  $\geq$  Grade 3 AE is 2.5%, the probability of study suspension under the above rule is approximately 0.01; if the true probability is 40%, the probability of suspension is approximately 0.91 (probabilities estimated from 5,000 simulations).

If this rule is met, further treatment for all subjects enrolled will be immediately halted. A safety evaluation will be performed and reviewed with the FDA and DMC prior to resuming any drug.

We are using a Simon's two-stage design (Simon, 1989) to stop early for futility. Based on the null hypothesis of 6% ORR and alternative hypothesis of 26% ORR, with a 1-sided alpha of 0.05, in the first stage, 12 subjects will be accrued. If there are 0 responses in these 12 subjects, then study will be stopped for futility. Otherwise, 8 or more additional subjects will be accrued for a total of 20 subjects. The null hypothesis will be rejected if 4 or more responses are observed in 20 subjects. This design (minimax) yields a type I error rate of 0.05 (one-sided) and power of 80%.

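### Four of the five toxicity stopping counts do not meet the plan's own criterion (lower 80% bound above 20%) at their stated limits, and the 0.91 suspension probability does not reproduce

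*Combined protocol and SAP*

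**What the plan says.** Sections 6.1 and 16.4 carry the same rule. It has three parts.

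- **Criterion.** "the study incorporates a stopping rule if the lower bound of a 1-sided 80% exact binomial confidence interval of the discontinuation rate", for medically significant Grade 3 or higher events "that are possibly, probably, or definitely attributable to the drug is > 20" percent.
- **Counts.** The criterion is then turned into a list: "Operationally, any of the following would trigger such a rule: 2 out of the first" 6 or fewer subjects, 3 of the first 9 or fewer, 4 of 13, 5 of 16, or 6 of 20.
- **Operating characteristics.** At a true rate of "2.5%, the probability of study suspension under the above rule is approximately 0.01"; and "if the true probability is 40%, the probability of suspension is approximately 0.91 (probabilities estimated from 5,000 simulations").

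If the rule is met, treatment stops for all enrolled subjects until the FDA and the DMC have reviewed a safety evaluation. Section 5.5 gives a total accrual of 20.

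**The concern.** The list is offered as the working form of the criterion, so each listed limit should be the largest denominator at which that number of events still puts the exact lower bound above 20%. Two events in six subjects looks too few for that, which prompted a check of every limit and of the two quoted probabilities.

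At stake is a mandatory halt of treatment for everyone on study. If the formula and the list disagree, the investigator and the DMC have two answers at the same data and no statement of which governs. Someone who recalculates the bound after 2 events in 6 subjects could conclude that the halt was not required. The quoted probabilities are also what a committee would use to judge whether the rule is strict enough.

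**Working it through.** **Inputs** (sections 6.1, 16.4 and 5.5): one-sided 80% exact bound; threshold 20%; listed limits 2/6, 3/9, 4/13, 5/16, 6/20; stated suspension probabilities 0.01 at 2.5% and 0.91 at 40%, from 5,000 simulations; at most 20 subjects.

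**Step 1. The plan's probabilities.** Treat subjects as independent, each with event probability p, and follow the cumulative count through 20 subjects. Suspension occurs the first time the count reaches r with n no greater than the limit listed for r. An exact recursion gives:

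| True rate | Stated | Exact, listed counts |
|---|---|---|
| 2.5% | 0.01 | 0.0091 |
| 40% | 0.91 | 0.9418 |

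Checking after every subject, or only at n = 6, 9, 13, 16 and 20, gives the same values. A fresh 5,000-run simulation gave 0.0088 and 0.942. The first stated figure reproduces, which supports this reading of the rule; the second does not.

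Monte Carlo error does not explain the gap. With 5,000 runs the standard error is √(0.91 × 0.09 / 5,000) = 0.0040, so the gap of 0.9418 − 0.91 = 0.0318 is 7.9 standard errors. Taking the error at the exact value instead, √(0.9418 × 0.0582 / 5,000) = 0.0033, makes it 9.6.

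**Step 2. The listed limits against the criterion.** The exact (Clopper-Pearson) one-sided 80% lower bound for x events in n subjects is the 0.20 quantile of Beta(x, n − x + 1). It exceeds 20% only when P(X ≥ x | n, p = 0.20) is below 0.20.

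| Listed limit | Lower bound | P(X ≥ x) at p = 0.20 | Above 20%? |
|---|---|---|---|
| 2/6 | 0.1399 | 0.345 | No |
| 3/9 | 0.1757 | 0.262 | No |
| 4/13 | 0.1822 | 0.253 | No |
| 5/16 | 0.1994 | 0.202 | No (just) |
| 6/20 | 0.2013 | 0.196 | Yes |

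**Step 3. The counts the criterion implies.** The largest qualifying denominators are 2/4 (0.212), 3/7 (0.228), 4/11 (0.217), 5/15 (0.213) and 6/20 (0.201). The two rules therefore disagree at seven points: 2/5 (0.169), 2/6, 3/8 (0.1986), 3/9, 4/12 (0.1979), 4/13 and 5/16.

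**Step 4. What the difference does.** Exact suspension probability, checked after every subject:

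| True rate | Listed counts | Criterion's counts |
|---|---|---|
| 2.5% | 0.009 | 0.004 |
| 10% | 0.134 | 0.073 |
| 20% | 0.460 | 0.347 |
| 40% | 0.942 | 0.917 |

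**Step 5. Could another reading rescue the figures?** One-sided levels from 60% to 95% and Wilson, Wald, Jeffreys and mid-P bounds were tried; none yields the listed set as its boundaries. The Jeffreys bound does exceed 0.20 at all five listed limits, but the plan specifies an exact interval. Two variants come close to 0.91. Applying the criterion literally gives 0.917 at 40%, but then 0.004 rather than 0.01 at 2.5%. Dropping the 6/20 look gives 0.9175 and 0.009, but that look is in the text.

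**The case against.** The arithmetic is not in dispute; the case on the other side is about weight.

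- **The text points to the list.** The counts are introduced as the operational form, and a committee would normally use them rather than compute exact bounds. That is fair, but the list is presented as following from the criterion, and the plan does not say which prevails where they differ.
- **The mismatch is protective.** The listed counts stop earlier, a halt can be lifted after review, and a separate rule covers possibly drug-related deaths. This stands: no subject is under-protected, and the efficacy test is untouched. The cost is extra suspensions and an ambiguous trigger.
- **The failures are at the upper limits only.** This also stands. At 2/4, 3/7, 4/11, 5/15 and smaller denominators the two rules agree. Of the seven discrepant points, 3/8, 4/12 and 5/16 miss by about 0.2 percentage points or less. The clear misses are 2/5, 2/6, 3/9 and 4/13.
- **0.91 is near the criterion's 0.917.** True: that gap is within about two Monte Carlo standard errors. But the criterion's own counts give 0.004 at 2.5%. The listed counts match 0.01 but not 0.91, so neither rule reproduces the stated pair.
- **The event definitions also differ.** The criterion refers to discontinuations due to such events; the list counts unacceptable toxicity or Grade 3 or higher drug-related events. The comparison above takes the event to be the same in both. This is a further reason to reconcile the two statements.

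**Conclusion.** The concern holds. At their stated limits, four of the five counts fail the plan's own criterion, with lower bounds of 14.0%, 17.6%, 18.2% and 19.9% against a required value above 20%. The suspension probability at a 40% rate is 0.942 for the rule as listed, not 0.91. The choice of rule moves the suspension probability by 6.1 percentage points at a true rate of 10% (13.4% against 7.3%) and by 11.3 points at 20% (46.0% against 34.7%).

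These results assume independent subjects with a common event probability, one event definition for both rules, and evaluation as each subject's outcome becomes known. The fault is an internal contradiction in a mandatory halt and a wrong operating characteristic; it is not a loss of safety. It must be corrected because the text decides when treatment stops for every subject. This review does not say which rule is clinically right.

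**What to change.** The sponsor and its safety committee should decide which rule governs and make the criterion, counts and probabilities agree in both 6.1 and 16.4.

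- **If the criterion stands:** list 2 of 4 or fewer, 3 of 7, 4 of 11, 5 of 15 and 6 of 20, with suspension probabilities of 0.004 at 2.5%, 0.347 at 20% and 0.917 at 40%.
- **If the list stands:** re-describe the criterion so that it no longer claims an exact 80% lower bound above 20%, and state 0.009 at 2.5%, 0.460 at 20% and 0.94 at 40%.

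In either case, report exact rather than simulated values, include a rate near 20% so that the committee can see how the rule behaves at its own threshold, and use one definition of the counted event throughout. The cost is wording and recomputed figures in two sections; no patients, visits or data are added.

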**16.0 STATISTICAL CONSIDERATIONS****16.1 Study Design**

The primary objective of the study is to determine the efficacy of nivolumab as measured by the overall response rate (ORR), in subjects with hematologic malignancies with relapsed or refractory disease after receipt of CAR T-cell therapy. ORR will be estimated, and its corresponding 95% exact binomial CI will be provided. The analyses of time-to event endpoints (DOR, PFS, and OS) will follow standard methodology by employing Kaplan-Meier and Cox proportional hazard model methodology.

Safety data will be summarized descriptively. Adverse events will be summarized by severity, seriousness, and relationship to study drug. Laboratory data will be compared to baseline values.

Additional exploratory data analyses will be conducted as appropriate.

The primary objective will be investigated by assessing if the true ORR is at least above some desirable target level following therapy with nivolumab. A subject is classified as response evaluable if they have at least one response assessment or if they discontinue from treatment due to death from any cause prior to obtaining at least one response assessment.

Based on the observations in Ansell 2018, the ORRs were low, e.g., 10% and 3% in the auto-HCT-failed and auto-HCT-ineligible, respectively. The desire is therefore to rule out a 5% ORR which will require around 25% ORR. If the sample size is 20, the study will have 85% power to detect the difference between the Null hypothesis of 5% ORR and the Alternative of 25% ORR, with a 1-sided alpha of 0.05.

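### The primary ORR test has two null values, 5% in Section 16.1 and 6% in Section 16.4, and Section 16.3 names neither; the p-value and the ORR claimed as ruled out depend on the choice, but the verdict at 20 subjects does not

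*Combined protocol and SAP*

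**What the plan says.** Three places in the combined protocol and SAP bear on the primary test of ORR.

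- Section 16.1 (Study Design) sets the aim: "The desire is therefore to rule out a 5% ORR which will require around 25% ORR". It then says that, with 20 subjects and a one-sided alpha of 0.05, "the study will have 85% power to detect the difference between the Null hypothesis of 5% ORR and the Alternative of 25% ORR".
- Section 16.3 (Statistical Consideration) prescribes the test, "using an exact binomial test for single proportion at the 5% one-sided significance level if appropriated", and gives no null value.
- Section 16.4 (Stopping rules for toxicity and futility) starts from a different pair: "Based on the null hypothesis of 6% ORR and alternative hypothesis of 26% ORR". The stage 1 rule is "If there are 0 responses in these 12 subjects, then study will be stopped for futility", and the final rule is "The null hypothesis will be rejected if 4 or more responses are observed in 20 subjects". The stated properties are a one-sided type I error of 0.05 and 80% power.

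No section says which null governs the test in 16.3. No cut-off is given for an analysed number other than 20. Such a number is not excluded: Section 9.0 calls the enrolment approximate, Section 16.1 defines a response-evaluable subset, and Section 16.4 speaks of eight or more further subjects while keeping the total at 20.

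**The concern.** A test of one proportion is not defined until its null value is fixed. An analyst following 16.1 would report a p-value against 5% and say that 5% had been ruled out. An analyst following 16.4 would report a larger p-value against 6% and make a different claim. Both could cite the plan. The trial is open-label with one arm, so responses are seen as they accrue. A null left open until the analysis is a freedom on the primary endpoint that the plan should not leave.

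**Working it through.** **Inputs.** Section 16.1: p0 = 0.05, p1 = 0.25, n = 20, one-sided alpha 0.05, power 85%. Section 16.4: p0 = 0.06, p1 = 0.26, stop if 0 of 12, reject if at least 4 of 20, power 80%. Section 16.3: exact binomial test, one-sided 5%.

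**1. The plan's own figures.** For the two-stage rule,

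P(reject | p) = Σ (x = 1 to 12) P(X1 = x) · P(X2 ≥ max(4 − x, 0)), with X1 ~ Bin(12, p) and X2 ~ Bin(8, p).

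| p | P(reject) |
|---|---|
| 0.06 | 0.0286 |
| 0.26 | 0.8003 |
| 0.05 | 0.0157 |
| 0.25 | 0.7712 |

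The 80% power in 16.4 is reproduced for 6% against 26%. The 0.05 there is the nominal limit; the attained rate is 0.029. An exhaustive search (alpha at most 0.05, power at least 80%) returns 0/12 then 4/20 as the minimax design for 6% against 26%. For 5% against 25% it returns a different design, 0/12 then 3/16. The rule in 16.4 therefore belongs to the 6% pair.

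The 85% in 16.1 is reproduced by the arcsine approximation: Φ{2(asin √0.25 − asin √0.05)√20 − 1.645} = Φ(2.666 − 1.645) = Φ(1.021) = 0.846. The exact one-stage test at 4 of 20 has power 0.775 for the same pair.

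**2. The p-value at n = 20.** P(X ≥ x | n = 20, p0), one-stage exact:

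| Responses | Null 5% | Null 6% |
|---|---|---|
| 3 | 0.0755 | 0.1150 |
| 4 | 0.0159 | 0.0290 |
| 5 | 0.0026 | 0.0056 |

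The smallest rejecting count is 4 under both. The p-value at that count nearly doubles (0.0290 / 0.0159 = 1.8).

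**3. The verdict at other analysed numbers.** The smallest x with P(X ≥ x) ≤ 0.05, one-stage exact:

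| n | Null 5% | Null 6% |
|---|---|---|
| 12-14 | 3 | 3 |
| 15-16 | 3 | 4 |
| 17-23 | 4 | 4 |
| 24-28 | 4 | 5 |
| 29-30 | 5 | 5 |

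Results at which the verdict splits (5% null, then 6% null): 3/15 gives 0.0362 and 0.0571; 3/16 gives 0.0429 and 0.0673; 4/24 gives 0.0298 and 0.0526; 4/28 gives 0.0491 and 0.0841.

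**4. Allowing for the stage 1 stop.** With the formula in step 1 and the second stage set to n − 12, the cut-offs over n = 13 to 30 differ at n = 15-17 (3 against 4) and n = 24-29 (4 against 5). The two added sizes are borderline under the 5% null: 3/17 gives 0.0496 and 4/29 gives 0.0500. From n = 18 to 23 the cut-off is 4 under both nulls by either method.

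**The case against.** The strongest reply is that Section 16.4 fixes the decision in advance, at 4 or more of 20, and that this rule keeps the one-sided error below 5% under either null (0.016 and 0.029). That stands. A reader might infer from the two nulls that a result could be declared positive under one section and negative under the other, or that the verdict is open whenever the analysed number is not 20. The documents do not support either reading near the planned size: losing two subjects or gaining three changes nothing.

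The affected sizes are also far from the plan. An analysed number of 15 or 16 needs 4 or 5 of 20 subjects to be non-evaluable, yet Section 16.1 counts a death before the first assessment as evaluable, and it does not say that the primary test is limited to evaluable subjects. A number of 24 to 28 needs 4 to 8 subjects beyond a total given as 20 in the synopsis, Section 5.5 and Section 16.5. Even there, only one response count splits.

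A second reply is that 5% is the only null with a stated rationale: 16.1 derives it from ORRs of 10% and 3% in an earlier nivolumab study, while 16.4 gives no reason for 6%. That is fair, and using 5% throughout would be coherent. But the power in 16.4 would then have to be restated as 77%, because 0/12 and 4/20 gives 0.771 for 5% against 25%.

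Neither reply says which p-value is to be reported, or which ORR has been excluded, at exactly 20 subjects. The point estimate and 95% exact interval do not depend on the null, but they do not settle the claim: at 4/20 the lower limit is 5.7%, above 5% and below 6%. That is not a contradiction with rejecting 6%, since the limit corresponds to a one-sided 2.5% test, but it shows that the two claims differ.

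**Conclusion.** The inconsistency is real, and nothing in the documents resolves it. At the planned size its effect is on reporting: a p-value of 0.016 or 0.029 at 4/20, and a claim to have excluded 5% or 6%. The accept-or-reject decision at 20, and at 18 to 23, does not depend on it. A change of verdict is confined to 3 of 15-16 or 4 of 24-28 by the one-stage test (3 of 15-17 or 4 of 24-29 with the stage 1 stop), within the range up to 30. These figures assume an exact one-sided test at 5% and, for the two-stage results, that stage 1 stays at 12 subjects with the 0/12 stop.

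It should be corrected because the null is part of the definition of the primary test, but it is not a threat to the trial's planned decision.

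**What to change.** Use one null and alternative pair in Sections 16.1, 16.3 and 16.4. The 6% against 26% pair needs the least change, because the 0/12 and 4/20 rule already delivers its stated 80% power for that pair. In detail:

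- In 16.3, state that the exact test is of the null hypothesis ORR ≤ 6%.
- In 16.1, replace the 5% against 25% pair and remove the 85% power statement that goes with it. Add a sentence giving the reason for 6%.
- In 16.3 or 16.4, state that if the analysed number is not 20, the cut-off is derived from that same 6% null, allowing for the 0/12 stop.

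The cost is wording only. Sample size, futility rule and the 4/20 cut-off are unchanged. The downside is a slightly less favourable p-value: 0.029 instead of 0.016 at 4/20.

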### **5.5 Estimated Accrual**

Estimated accrual for this trial is 20 subjects with hematologic malignancies over 36 months

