## **9.0 STUDY INTERVENTIONS**

[figure not shown]
This is a single arm, unblinded phase II trial of nivolumab, a PD-1 inhibitor, for treatment of patients with hematologic malignancies (including B-cell non-Hodgkin lymphoma, chronic lymphocytic leukemia, and multiple myeloma) who either experience relapse or have persistent disease after treated with CAR T-cell therapy.

Approximately 20 subjects will be enrolled on this study, which will include a screening phase, an active treatment phase, and a follow-up phase. Before any study-related procedure can be performed, all

subjects must sign an informed consent form (ICF). Subjects will be evaluated for eligibility at screening.

The active treatment phase will extend from cycle 1, day 1, until study treatment discontinuation due to disease progression, initiation of subsequent anti-cancer therapy, unacceptable toxicity, withdrawal, or completion of study treatment. A study schema is depicted in figure 1.

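### Section 16.4 reports the 0.05 design ceiling as the type I error its two-stage rule yields (attained: 0.029), and gives a second-stage size that contradicts its own total of 20

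*Combined protocol and SAP*

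**What the plan says.** Section 16.4 sets out a Simon two-stage design. The inputs are "Based on the null hypothesis of 6% ORR and alternative hypothesis of 26% ORR, with a 1-sided alpha of 0.05". For stage 1, "in the first stage, 12 subjects will be accrued". The futility rule is "If there are 0 responses in these 12 subjects, then study will be stopped for futility". For stage 2, "Otherwise, 8 or more additional subjects will be accrued for a total of 20 subjects". The decision rule is "The null hypothesis will be rejected if 4 or more responses are observed in 20 subjects". The section then states the operating characteristics: "This design (minimax) yields a type I error rate of 0.05 (one-sided) and power of 80" per cent.

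Elsewhere the total is 20. The synopsis gives 20 trial subjects, the enrolment table in Section 16.5 adds up to 20, and Section 5.5 says "Estimated accrual for this trial is 20 subjects with hematologic malignancies over 36 months". Section 9.0 is looser: "Approximately 20 subjects will be enrolled on this study".

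Two other statements bear on the point. Section 16.1 defines a response-evaluable subject as one with at least one response assessment, or one whose treatment ended through death before any assessment. Section 16.3 plans an exact one-sided binomial test of ORR at 5%, qualified by whether it is appropriate, and does not name the null value.

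**The concern.** These few sentences are the trial's only rule for declaring efficacy, so the sample size, cut-off and error rates in them should agree with one another.

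They do not agree in two places. A two-stage design with small integer cut-offs rarely attains its nominal alpha exactly, so a yielded rate of exactly 0.05 needs checking. The boundaries of such a design also belong to fixed stage sizes, and a second stage of eight or more does not fit a total of 20.

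The first error affects how the result is reported. The second leaves the decision undefined if the number analysed is not 20. That could happen: a subject who withdraws or stops for toxicity before the first assessment is not response-evaluable under Section 16.1, and Section 16.4 does not say whether its 12 and 20 are enrolled or evaluable subjects, or whether subjects are replaced.

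**Working it through.** **Inputs (all Section 16.4).** Null p0 = 0.06; alternative p1 = 0.26; stage 1 n1 = 12, stop at 0 responses; total n = 20; reject at 4 or more.

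**Formula.** With X1 ~ Bin(12, p) and X2 ~ Bin(n − 12, p) independent,

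P(reject) = Σ over x = 1 to 12 of P(X1 = x) × P(X2 ≥ 4 − x).

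From x = 4 upward the second factor is 1.

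**Step 1: the plan's own figures, n = 20.**

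| Stage 1 responses | p = 0.06: P(X1) × P(X2 ≥ 4 − x) | p = 0.26: P(X1) × P(X2 ≥ 4 − x) |
|---|---|---|
| 1 | 0.36453 × 0.00962 = 0.00351 | 0.11369 × 0.34652 = 0.03939 |
| 2 | 0.12797 × 0.07916 = 0.01013 | 0.21969 × 0.65733 = 0.14441 |
| 3 | 0.02723 × 0.39043 = 0.01063 | 0.25729 × 0.91008 = 0.23416 |
| 4 or more | 0.00434 | 0.38237 |
| **Sum** | **0.0286** | **0.8003** |

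Power reproduces the stated 80%. Type I error is 0.0286, not 0.05; the ratio is 0.05 / 0.0286 ≈ 1.7.

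**Step 2: where the 0.05 comes from.** Lowering the cut-off to 3 of 20 gives a type I error of 0.1104, so 4 is the smallest cut-off that keeps the error at or below 0.05. A search over designs with alpha ≤ 0.05 and power ≥ 0.80 for 6% versus 26% returns the plan's design (0/12, then 4/20) as minimax. The 0.05 is therefore the search limit, and the gap down to 0.0286 comes from the discreteness of the binomial. The futility stop contributes almost nothing: without it the error is 0.0290.

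**Step 3: stage-size arithmetic.** 12 + 8 = 20 exactly. Any larger second stage gives a total above 20.

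**Step 4: what would follow if the number were not 20 and the cut-off stayed at 4.** This is a what-if; the plan does not instruct it.

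| n | Type I error, p = 0.06 | Power, p = 0.26 |
|---|---|---|
| 18 | 0.0200 | 0.726 |
| 19 | 0.0241 | 0.766 |
| 20 | 0.0286 | 0.800 |
| 21 | 0.0335 | 0.830 |
| 22 | 0.0388 | 0.855 |
| 23 | 0.0445 | 0.876 |
| 24 | 0.0505 | 0.894 |
| 25 | 0.0569 | 0.909 |
| 28 | 0.0778 | 0.939 |
| 30 | 0.0930 | 0.952 |

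The error first passes 0.05 at n = 24, four subjects over plan. With fewer than 20, power is lost instead.

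**Step 5: sensitivity to the null.** Section 16.1 works with a 5% null. Against 5% the same rule gives 0.0157 at n = 20 and 0.0286 at n = 24, and reaches about 0.050 only at n = 29.

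**Step 6: does the Section 16.3 test settle the matter at n = 24?** For 4 responses in 24, the exact one-sided p-value is 0.0526 against 6% (not rejected) and 0.0298 against 5% (rejected). Because Section 16.3 names no null, the answer is undetermined.

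**The case against.** The strongest reply is that nothing here harms the trial as planned. The sentence containing *or more* itself ends at a total of 20, the next sentence ties the cut-off to 20, and the synopsis, Section 5.5, Section 16.5 and the last toxicity boundary all use 20. *Approximately 20* in Section 9.0 is ordinary enrolment language. Quoting nominal alpha is common, and the error is in the safe direction. The phrase may also have been meant to leave room to reach 20 evaluable subjects, although Section 16.4 does not say so.

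Most of that stands, and it rules out two stronger readings. A reader might infer that the second stage is open-ended and that false-positive control is lost. The documents do not support this: no maximum above 20 appears anywhere, no passage applies the cut-off of 4 to a larger number, and up to three extra subjects would still leave the error below 0.05. The figures at 28 and 30 need 40% and 50% over-enrolment. A reader might also link the two errors and take 0.029 as a result of the loose stage size. It is not; 0.029 is the value at exactly 20.

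What the reply does not remove is that one sentence misreports an operating characteristic, setting a nominal limit beside an attained power as though both were attained, and that another contradicts itself. The Section 16.3 test is only a partial safeguard, as Step 6 shows.

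**Conclusion.** Both errors are real, small and independent of each other.

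1. The stated type I error of 0.05 is wrong as a yielded rate. Against the 6% null it is 0.029 one-sided. Power of 80% is right, the cut-off of 4 is right, and the design is a valid minimax design that is conservative at 20. No sample size or decision changes.

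2. The second-stage size contradicts the total, and no rule covers a number other than 20. Passing 0.05 requires two things the plan does not state: at least four subjects beyond 20, and the cut-off of 4 carried over to them.

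The figures assume independent responses with a common rate, the 6% null of Section 16.4 and the two-stage rule as written. The difference between the 5%/25% hypotheses of Section 16.1 and the 6%/26% of Section 16.4 is a separate matter. It affects these numbers only as shown in Step 5.

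**What to change.** In Section 16.4:

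- State the operating characteristics as a one-sided type I error of at most 0.05 (attained 0.029 against 6%) and power of 80% at 26%.
- Delete *or more*, so that stage 2 is 8 subjects for a total of 20.
- Say whether the 12 and the 20 are response-evaluable subjects as defined in Section 16.1.
- Add one sentence: if the number analysed differs from 20 in either direction, the cut-off is recomputed so that the exact two-stage type I error against the stated null stays at or below 0.05. Against 6%, a cut-off of 4 would still hold at 21 to 23 but not at 24.

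Rewording *approximately 20* in Section 9.0 is optional. The cost is a few sentences at the next amendment; no extra subjects and no change to the planned cut-off.
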